8.0 Costs and Compensation to Participants

Costs to Participants

Study related materials will be provided to the participants without charge. The Inpatient stays will be covered by a grant from the Vanderbilt Institute of Clinical and Translational Research (VICTR). Assay and testing costs will be covered by an NIH grant. The participants will be responsible for their own travel expenses to come to Vanderbilt and any extraneous expenses related to their time in Nashville.

Participant Compensation

Participants will be compensated at a rate of \$450 for the entire study (\$175 for each phase and an extra \$100 at completion). For patients with POTS, this may help to defray some of their travel expenses. For the healthy control subjects, this will compensate them for 2 stays on the CRC and 2 separate weeks of diet (which may not be pleasant). If participants are unable to finish the study or withdraw from the study, their compensation will be rated according to how much of the study they completed.

9.0 Reporting of Adverse Events or Unanticipated Problems involving Risk to Participants or Others

The P.I. and at least one co-investigator will review data from subjects enrolled in this study on a bi-monthly basis.

Adverse events will be monitored on an ongoing basis by Drs. [name] & [name] (both of whom will be responsible for tracking adverse events in this study). Any adverse event of a serious or greater nature will be reviewed immediately with the P.I.

The adverse event will be described with the following information: description of the event; outcome of the event; duration of the event; relationship to study procedure; requirement, if any, for treatment or intervention; and outcome.

Adverse events will be graded according to the following scale:

0 = No adverse event or within normal limits

1 = Mild adverse event (transient and mild in nature, and no treatment is necessary)

2 = Moderate adverse event (some intervention and treatment are necessary, but participant completely recovers

3 = Severe adverse event (an event that results in hospitalization, disability, or death or is life-threatening)

The investigator will state his opinion on whether there is a reasonable possibility that the event or experience is elated to a procedure performed as part of this study. Serious adverse events will be reported in writing to the Vanderbilt IRB within 72 hours of occurrence. All study adverse events will be summarized once a year, as part of the annual review report to the IRB.

10.0 Study Withdrawal/Discontinuation

The investigators or Vanderbilt may stop participants from taking part in this study at any time if it is in their best interest, if they do not follow the study rules, or if the study is stopped.

Participants are free to withdraw from this study at any time. We will cease to collect study information at the time of withdrawal of consent. Withdrawal of consent or refusal to participate will not prejudice their health care.

11.0 Statistical Considerations

Statistical Analysis Plan

Primary outcomes will be 24 hr urinary DA and sodium excretion. The primary analyses will involve a comparison of values for urine excretion as a result of a high-sodium or low-sodium diet and between patient and control groups. Secondary endpoints will include the change in plasma volume and measures of orthostatic tachycardia and orthostatic symptoms (VOSS). Differences will be assessed using a Student's t-test and Mann-Whitney U test for group comparisons and a paired t test and Wilcoxon signed rank test for diet comparisons. It is possible that the speed of achievement of sodium balance, as well as cumulative sodium balance, may provide additional information about sodium handling. A mixed-effects model will be developed to describe the time, diet and group effects.

Data will be entered into a Microsoft Excel spreadsheet or a CTSA generated, HIPAA compliant Research Data Capture (REDCap) web-based database 52. SPSS for Windows (version 17.0), *Stata 11.0*, and R (www.r-project.org) will be used for data analysis. The sample size calculations were performed using the software package PS Power and Sample Size Calculations version 3.0.1 53. A co-investigator on this grant, [name] PhD, Professor of Biostatistics at Vanderbilt University, will be primarily responsible for the statistical analyses of this study.

Sample Size

Based on a standard deviation of 35 mEq for urinary sodium excretion in a group of 87 normal volunteers on our moderate-sodium diet, a sample size of 17 subjects in each group will have 80% power to detect a difference of 35 mEq with a 0.05 two-sided significance level. A difference of 0.56 μ moles urinary DA will be detectable based on a standard deviation of 0.56 μ moles from our laboratory. Twenty healthy volunteers and 20 POTS patients will be enrolled to allow for data loss and subject dropout.

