predominantly in young women. POTS is a chronic condition of consistent orthostatic tachycardia (> 30 bpm increase) and symptoms that are worse on standing but relieved by lying down. Orthostatic symptoms include palpitations, lightheadedness, chest pains, dyspnea, tremulousness, blurred vision, and mental clouding. When studied in balance on 150 mEq sodium/day, many patients with POTS have a low plasma volume. Furthermore, POTS patients have inappropriately low plasma renin activity and aldosterone for their level of

hypovolemia.

Physicians often prescribe a high sodium diet for the treatment of POTS. The rationale behind this approach is that sodium in the diet will help subjects to retain fluid, and thereby raise blood volume and/or blood pressure. We will compare urinary DA and sodium responses to low and high dietary sodium intake in POTS and controls. Assessment of urinary catechols under these circumstances, well developed in our laboratory, permits a legitimate characterization of renal DA production and its metabolites since these collectively represent an index of DA synthesis in the kidney. Urine will be collected for 24hr intervals throughout the study for analysis of

creatinine, electrolytes, and catecholamines, so that we can look at differences during transitional periods as well as during sodium balance. Plasma levels of DOPA and catechols allow us to assess DOPA available to the kidney, as well as the amount of sympathetic stimulation. We will also measure plasma renin activity (PRA) and aldosterone.

We have preliminary evidence that a high salt diet raises plasma volume (as determined by changes in hematocrit) and blunts the tachycardia with standing. This treatment is also felt to decrease symptoms in some patients with POTS. We will now use the DAXOR BVA-100 Blood Volume Analyzer to test whether patients with POTS have a blunted plasma volume expansion in response to a high sodium diet and assess whether raising the amount of sodium consumed in the diet can lessen orthostatic symptoms in POTS. We will look at associations between alterations in urinary sodium and DA and changes in plasma volume.

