2.0 Rationale and Specific Aims

Patients with POTS may not adequately expand their plasma volume in response to a high sodium diet. Mechanisms involved in the regulation of plasma volume, such as the renin-angiotensin-aldosterone system and renal DA, may be impaired in POTS and may respond inappropriately to changes in dietary sodium. The purpose of this study is to determine (1) whether changes in dietary sodium level appropriately influence sodium excretion in POTS; (2) whether changes in dietary sodium level appropriately influence DA excretion in POTS; (3) whether a high dietary sodium level appropriately expands plasma volume in POTS; and (4) whether patients with POTS have improvements in their orthostatic tachycardia and symptoms as a result of a high dietary sodium level.

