6.0 Study Procedures

Participants will be given a screening medical exam, including a pregnancy test, 12 lead ECG in supine and upright positions, and blood for a CBC and a Comprehensive Metabolic Panel. If the pregnancy test is positive, the subject will not continue with the study. Patients will often be identified from a prior assessment at the Vanderbilt Autonomic Dysfunction Center. Screening procedures, other than the pregnancy test, will not be repeated if results are available from within the previous 3 months. Individuals shown to be an appropriate candidate for the study will be told to abstain from medications that could affect blood pressure or blood volume for at least 3 days prior to and during admission for the study. Individuals who take such medication routinely will not be included in the control group. Patients with POTS will be advised to consult

their primary care physician before stopping any medication and to contact the Principal Investigator or an Autonomic nurse if any problems occur prior to admission. Approved participants will be studied on an experimental diet with a fixed amount of sodium consumed per day (confirmed by analysis of 24hr urine sample) and will consume no substances that interfere with catecholamine synthesis, release or assay.

- Pre-study assessments include: H&P, CBC, Comprehensive Metabolic Panel, pregnancy test, 12 lead ECG in supine and upright positions
- 3-day drug withdrawal of any medication with the potential to influence blood pressure
- Day 1: start 150 mEq sodium diets. Diets will contain 60-80 mEq potassium, be free of methylxanthines and low in monoamines and provided by the kitchen of the Clinical Research Center (CRC). The study participants will need to drink 1.5-2 liters of water per day to ensure they are well hydrated. Participants will document that they consumed all food provided by the kitchen and no other food.
 - Start 24 hr urine collection for sodium, potassium, creatinine, and catechols.
 - POTS patients will generally be admitted to the CRC on Day 1, whereas normal volunteers will do initial part of study as outpatients.
- Days 2-5: 10 mEq or 300 mEq sodium diet in a random order starting after 3 meals of 150 mEq Na/day diet. Must consume 1.5-2.0 liters/day of water.
 - Continue daily 24 hr urine collections for sodium, potassium, creatinine, and catechols.
- Day 5: Start 24hr Holter combined ECG monitor and BP monitor

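### For urinary sodium and DA the question is whether the response to diet differs between POTS and controls, but the named tests compare values; the between-group test of change is not named and its power is not documented.

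*Combined protocol and SAP*

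**What the plan says.** Section 1.0 states the question for the two urinary outcomes: "We will compare urinary DA and sodium responses to low and high dietary sodium intake in POTS and controls". Aims 1 and 2 in Section 2.0 ask "whether changes in dietary sodium level appropriately influence sodium excretion in POTS" and "whether changes in dietary sodium level appropriately influence DA excretion in POTS". Each participant takes both the 10 and the 300 mEq diet, in random order (Sections 5.0 and 6.0).

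Section 11.0 makes 24 hr urinary DA and sodium the primary outcomes and describes the primary analyses as a "comparison of values for urine excretion as a result of a high-sodium or low-sodium diet and between patient and control groups". The tests are Student's t and "Mann-Whitney U test for group comparisons and a paired t test and Wilcoxon signed rank test for diet comparisons". It then adds: "A mixed-effects model will be developed to describe the time, diet and group effects". No group-by-diet term is mentioned, and the model is not called primary.

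The sample size rests on a single spread: "Based on a standard deviation of 35 mEq for urinary sodium excretion in a group of 87 normal volunteers on our moderate-sodium diet". It claims 80% power with 17 per group for a 35 mEq difference at two-sided 0.05, gives a DA difference of 0.56 micromoles as detectable with an SD of 0.56, and enrols 20 per group. No SD on the 10 or 300 mEq diet, no within-person correlation and no SD of change is given.

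**The concern.** Sections 1.0 and 2.0, read together, ask for a between-group difference in within-person change. Unpaired tests of values and paired tests within each group do not estimate that quantity.

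- The sodium paired tests largely show that the diets were eaten. The diets are 290 mEq/day apart, and Section 6.0 uses the same urine as the intake check: "a fixed amount of sodium consumed per day (confirmed by analysis of 24hr urine sample".
- For DA, significance in one group and not in the other is not evidence that the responses differ.
- A group test on one diet cannot separate a gap present on both diets from a different response.

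At stake is which result answers Aims 1 and 2. With several tests listed and none designated for the response question, that could be settled after the data are seen.

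**Working it through.** **Inputs from Section 11.0.** Sodium SD 35 mEq and difference 35 mEq; DA SD 0.56 and difference 0.56 micromoles; two-sided alpha 0.05; 17 per group needed and 20 enrolled. All other SDs, correlations and effects below are assumptions.

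**1. The plan's own figure.** For an unpaired comparison of values, d = 35/35 = 1.0. The t-based solution is 16.7, rounded up to 17 per group. Power is 80.7% at 17 and 86.9% at 20. DA also has d = 0.56/0.56 = 1.0, with the same result. The stated arithmetic is correct.

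**2. Power of the contrast.** The SD of change is √(sL² + sH² − 2·r·sL·sH), where sL and sH are the SDs on the low and high diets and r is the within-person correlation. Example: sL = sH = 35 and r = 0 give √2450 = 49.5, so d = 35/49.5 = 0.71 and power is 51.6% at 17 per group. Power for a 35 mEq difference in response (noncentral t):

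| sL, sH (mEq) | r | SD of change | Power, 17/group | Power, 20/group | Detectable at 80%, 17/group (mEq) |
|---|---|---|---|---|---|
| 35, 35 | 0 | 49.5 | 51.6% | 58.7% | 49.1 |
| 35, 35 | 0.5 | 35.0 | 80.7% | 86.9% | 34.7 |
| 35, 35 | 0.75 | 24.7 | 97.9% | 99.2% | 24.5 |
| 5, 35 | 0 | 35.4 | 79.9% | 86.2% | 35.0 |
| 5, 35 | 0.75 | 31.4 | 88.3% | 92.9% | 31.1 |
| 15, 35 | 0 | 38.1 | 73.8% | 80.9% | 37.7 |
| 15, 35 | 0.75 | 25.7 | 97.0% | 98.7% | 25.5 |
| 5, 50 | 0 | 50.2 | 50.4% | 57.4% | 49.8 |
| 5, 50 | 0.75 | 46.4 | 56.9% | 64.3% | 46.0 |
| 15, 50 | 0 | 52.2 | 47.5% | 54.2% | 51.7 |
| 15, 50 | 0.75 | 40.0 | 69.6% | 76.9% | 39.6 |

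For DA, with SD 0.56 assumed on both diets, the difference in response detectable at 17 per group is 0.78, 0.55 and 0.39 micromoles at r = 0, 0.5 and 0.75.

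**3. Sodium paired tests.** Assume true changes of 145 mEq in controls (half of the 290 mEq gap) and either 145 or 110 mEq in POTS. Even with the largest SD of change above, the noncentrality for 110 mEq is 110/52.2 × √17 = 8.7, against a critical t of 2.12 on 16 df. In simulation (40,000 trials per setting, 17 per group) both paired tests were significant in 100% of trials in either case. The contrast rejected in about 5% when the responses were equal.

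**4. DA, gap on both diets.** Assume POTS and controls differ by 0.56 micromoles on both diets, with SD 0.56 and identical responses. The group test on either diet has d = 1.0 and is significant in about 81% of trials at 17 per group. The contrast rejects in about 5% for r from 0 to 0.75.

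**5. DA, paired tests that disagree.** With identical true responses and paired-test power p in each group, the chance that exactly one is significant is 2p(1 − p).

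| Standardised effect | p, 17/group | Disagree, 17/group | p, 20/group | Disagree, 20/group |
|---|---|---|---|---|
| 0.5 | 0.491 | 50% | 0.565 | 49% |
| 0.72 | 0.796 | 32% | 0.863 | 24% |
| 0.85 | 0.908 | 17% | 0.950 | 9.5% |
| 1.0 | 0.972 | 5.5% | 0.989 | 2.3% |

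**The case against.** The strongest reply is that the contrast is available and merely not spelled out. The listed group tests also serve a secondary endpoint defined as the change in plasma volume, so a group test of within-person change is within the plan's vocabulary. The mixed model, with daily urine data behind it, could carry an interaction. This stands as far as it goes: a reader who inferred that the trial cannot test its question, or that the plan rules the test out, would go beyond the documents. But Section 11.0 speaks of change for that secondary endpoint and of values for the primary outcomes, and it designates neither route.

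The aims themselves name no controls. That is true; the between-group reading needs the Background sentence as well. That sentence is explicit, and controls are the only reference the design provides for judging a response appropriate.

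On sodium, if excretion on 10 mEq is near its floor in both groups, the group test on the 300 mEq diet comes close to the contrast. This stands, and it narrows the harm. It does not carry over to DA, and the plan does not name that test as the answer to Aim 1.

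On size, 50% is the mathematical maximum of 2p(1 − p), and the documents give no DA diet effect; at large effects the risk is small. The low power figures need either low correlation with equal SDs or a high-diet SD of 50 that appears in no document. Both points stand.

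**Conclusion.** The concern holds as a gap in what is named and documented. The tests stated for the primary outcomes do not by themselves answer the response question; the test that would is permitted but not specified. The practical harm falls mainly on DA: about 81% significant single-diet group tests from a gap unrelated to diet response, and one-group-only significance in up to 50% of trials, falling to 5.5% at a standardised effect of 1.0 with 17 per group.

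A reader might infer that the trial is underpowered or that the 17 per group is miscalculated. Neither follows. The figure reproduces for a comparison of values, and it also serves the contrast if the SD is 35 on both diets and r = 0.5. At 17 per group, contrast power for 35 mEq is 52–98% (SD 35 on both diets), 74–97% (low-diet SD 5–15, high-diet 35) or about 47–70% (low-diet 5–15, high-diet 50), for r from 0 to 0.75. The detectable difference is about 24–52 mEq. These ranges rest wholly on assumed SDs and correlations, take the SDs as equal in the two groups, and ignore the one degree of freedom spent on diet order. The plan should be corrected, but the design already collects the data required.

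**What to change.** In Section 11.0, name one primary test for urinary sodium and for DA: a two-sample comparison, POTS against control, of each participant's 300-minus-10 mEq change in 24 hr excretion from the collection at the end of each diet, adjusted for diet order. Use the planned mixed model as support, adding a group-by-diet term and keeping the day-within-diet time effect, with period and a random participant effect. Keep the separate group and paired tests as descriptive. Restate the detectable difference for the contrast at the planned size, giving the assumed SD of change, or the SD on each diet and the correlation that imply it.

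The cost is wording and one recalculation; no participants, visits or assays are added. The downside is that restated power may fall below 80% for 35 mEq, mainly if the SD on the 300 mEq diet is well above 35. In that case the plan should state the larger detectable difference.

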5.0 Enrollment/Randomization

The participants with POTS will be recruited from patients referred to the Vanderbilt University Autonomic Dysfunction Center. Healthy volunteers will be recruited from a population of previous participants in autonomic studies, through the ResearchMatch.org database, and through advertising and emails around the Vanderbilt community.

When contacting appropriate study candidates, the investigator will describe the complete protocol. The participants will then be given a written informed consent form that has been approved by the Vanderbilt Institutional Review Board. The subject will be given adequate time to read the consent form, ask questions, and if satisfied by the responses, sign the form. Consent or refusal to participate in this study will not affect medical care. No modifications or waiver of the elements of consent will be necessary in the execution of this study. Consent procedures will take place in the Autonomic Dysfunction Center at Vanderbilt University Medical Center.

Randomization tables will be used to determine whether the 10 mEq sodium/day or 300 mEq sodium/day diet will be consumed first.

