 - (1) predicted maximal heart rate is obtained,
 - (2) the respiratory exchange ratio reaches 1.15 or higher,
 - (3) oxygen consumption plateaus.
 - Verbal encouragement will be given to help subjects achieve a valid exercise test.
 - To assess VO₂ max directly, an individual's expired air is measured during exhaustive physical work.
 - The workload will be gradually increased on the bike by increasing the resistance. As the workload increases, oxygen consumption also increases. Throughout the test period exhaled air will be collected. When subjects can no longer continue, the test will be stopped.
 - Blood pressure will be measured at the end of each resistance-stage. Heart rate data will be recorded continuously.
 - Urine will be collected over the 2 hour period preceding the test and again over the 2 hours following the test.
 - Before and after completing the exercise test, subjects will be required to complete a "warm-up" and "cool-down" session including stretching exercises.
- Saline Bolus (optional)
 - Subject can receive an optional 2L saline bolus IV to prepare them for discharge to home
- Study Completed
 - Discharge Subject to home
- Discharge after testing

The same protocol will be performed with study diets providing 10 mEq sodium/day or 300 mEq sodium/day and 60-80 mEq potassium/day. The order of the diets will be randomly assigned.

To minimize variability due to phase of the menstrual cycle, each participant will undergo testing on the 2 diets during the same phase of the menstrual cycle.

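### Diet order is randomised, but the named tests have no period term and the plan does not say how order is balanced within POTS and controls

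*Combined protocol and SAP*

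**What the plan says.** Section 5.0 states: "Randomization tables will be used to determine whether the 10 mEq sodium/day or 300 mEq sodium/day diet will be consumed first". Section 6.0 repeats that "The order of the diets will be randomly assigned" and adds that "each participant will undergo testing on the 2 diets during the same phase of the menstrual cycle". Nothing is said about block size, or about separate lists for patients and controls.

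Section 11.0 sets the outcomes: "Primary outcomes will be 24 hr urinary DA and sodium excretion". Plasma volume change, orthostatic tachycardia and the symptom score (VOSS) are secondary. The tests named are "Student's t-test and Mann-Whitney U test for group comparisons" and, within persons, "paired t test and Wilcoxon signed rank test for diet comparisons". Straight after a sentence on how fast sodium balance is reached and on cumulative balance, the plan adds: "A mixed-effects model will be developed to describe the time, diet and group effects". It names no period, sequence or group-by-diet term, and does not say whether this model or the simple tests decide the primary comparison.

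**The concern.** Randomising order protects the diet contrast from a visit effect on average, but does not remove that effect from the data. Someone who takes low sodium first contributes a high-minus-low difference of diet effect plus period effect; someone who takes it second contributes diet effect minus period effect. A paired test treats that spread as random error.

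A period effect is plausible for some outcomes. Participation lasts 3–4 weeks (section 13.0), and each visit includes a stay on the research unit, a posture study, a self-rated symptom score and an exhaustive exercise test. Matching menstrual phase removes one source of between-visit difference, but not familiarity.

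Two things are at stake: power for the diet contrast, and the comparison of diet response between POTS and controls, which is what section 2.0 asks about. If the share starting on low sodium happened to differ between groups, a period effect would shift that comparison.

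**Working it through.** **The plan's own figure.** Two-sample t test, difference 35 mEq, SD 35 mEq, two-sided 0.05: exact power is 0.781 at 16 per group and 0.807 at 17. So 17 is reproduced. Dopamine (0.56/0.56) has the same standardised effect of 1. Enrolling 20 allows 3/20 = 15% loss.

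**Assumed, because the documents give no value.** Period effect π (second minus first visit), and within-person correlation ρ, taken from 0 to 0.7. Working in SDs of the within-person difference avoids choosing ρ. With SD 35 mEq on both diets, SD of the difference = 35 × √(2(1−ρ)): 49.5, 35.0 and 27.1 mEq at ρ = 0, 0.5 and 0.7.

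**Power of the diet test, n = 20 in one group.** The effect giving 80% paired-t power is 0.66 SD. With order 10:10, the paired test's expected variance is 1 + π² × n/(n−1). Power follows from the noncentral t with 19 df and noncentrality 0.66 × √20 / √(1 + π² × 20/19). A simulation with order fixed at 10:10 checks the approximation.

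| π (SD) | variance | power, formula | power, simulated |
|---|---|---|---|
| 0 | 1.000 | 80.0% | 80.1% |
| 0.25 | 1.066 | 77.5% | 78.1% |
| 0.5 | 1.263 | 70.3% | 72.5% |
| 0.75 | 1.592 | 60.3% | 62.4% |

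**With a period term.** The estimate is half the sum of the two order-group means of the high-minus-low difference, with standard error √((1/a + 1/b)/4) for an a:b split and 18 df, whatever π is:
- 10:10: SE 0.224, power 79.8%
- 12:8: SE 0.228, power 78%
- 14:6: SE 0.244, power 73%

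**Sodium diet contrast.** The diets differ by 300 − 10 = 290 mEq/day. If excretion follows intake, that is at least 290/49.5 = 5.9 SDs of the difference. Power is 1.000 with or without adjustment.

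**Order imbalance, only if allocation is simple 1:1.** From the Binomial(20, 0.5) distribution:
- a group splits 12:8 or worse with probability 0.50, and 14:6 or worse with probability 0.115;
- the two groups' shares starting on low sodium differ by 20 points or more with probability 0.27.

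**Effect of an imbalance in that trial.**
- Diet contrast within a group: π × (2p − 1), where p is the share starting on low sodium. At 12:8 this is 0.2π; at 14:6 it is 0.4π.
- Group comparison of change: 2π × (p₁ − p₂). A 20-point gap gives 0.4π. With π = 17.5 mEq (0.5 SD at ρ = 0.5) that is 7.0 mEq, or 0.2 SD.

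**Type I error of the paired test.** Over simple randomisation it is 0.049–0.051 for π of 17.5 or 35 mEq. Given a 14:6 split it is 0.076–0.119 at π = 17.5 and 0.129–0.190 at π = 35, across ρ from 0 to 0.7. With exact 10:10 order the test is conservative (about 0.03 at π = 0.5 SD).

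**The case against.** The planned tests are valid over the randomisation. A reader might infer that they are biased; they are not on average, and type I error stays at 5%. Bias needs both a real period effect and a realised imbalance. This stands.

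A reader might also infer that order is unbalanced within the two groups. Section 5.0 does not show that. A randomisation table can be blocked and can be separate for each group; the text neither says so nor rules it out. The 0.50 and 0.27 probabilities hold only for simple allocation.

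The period effects used are large beside the effect they are set against: 0.5 and 0.75 SD are 76% and 114% of 0.66 SD. At 0.25 SD the loss is 2–3 points, and at zero nothing is lost. The likeliest mechanisms concern posture and symptom measures, which are secondary. The primary outcomes are measured on kitchen-supplied diets after a 150 mEq lead-in day, and no period effect is documented for any outcome. These points limit the size of the concern but do not answer it for dopamine, plasma volume, tachycardia, VOSS or the group comparison of diet response.

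Finally, the mixed model may already include visit under *time*. That cannot be excluded, but the preceding sentence points to study day. Even on the generous reading, the model is not said to replace the paired tests, and it names no group-by-diet term.

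**Conclusion.** The point holds as a gap in specification that is cheap to close, not as a flaw that invalidates the analysis. The named tests ignore period in a design that randomises order. The cost in power depends on an unstated period effect: none at zero, 2–3 points at 0.25 SD, roughly 7–10 at 0.5 SD and 17–20 at 0.75 SD, for 20 participants and a diet effect set at 80% power. The sodium diet contrast loses nothing, and the stated sample size stands.

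If allocation is simple, there is a 27% chance of a gap in order of at least 20 points between groups. Given a period effect, such a gap shifts the group comparison of change by at least 0.4 times that effect in that trial, although the shift averages to zero over randomisation. The documents do not support saying that order is unbalanced, or that the planned tests are biased in general.

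**What to change.** 1. Base the diet and diet-response analyses on a mixed model with fixed diet, period, group and group × diet effects and a random person effect. The period-adjusted crossover t test is equivalent for the diet contrast; for the group comparison, regress each person's high-minus-low difference on group and order. Keep the paired t and Wilcoxon tests as supportive.
2. Say whether *time* means study day, diet period or both.
3. State how the order lists are made. If not already done, use separate blocked lists for POTS and controls.

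The cost is one degree of freedom (80.0% to 79.8% power at 10:10 when there is no period effect), a few sentences in section 11.0 and, if needed, new order lists. Blocking also protects the adjusted test, whose power falls to 78% at 12:8 and 73% at 14:6. The sample size need not change.
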